Glenohumeral Cortisone Injection

NCT04216017

[name]

Protocol

4/16/2018

Aim(s)

The primary objective of this study is to determine the feasibility of performing a large scale trial to address post traumatic decreased range of motion in patients with proximal humerus fractures.

Background and Significance

Shoulder stiffness is a known complication of proximal humerus fractures with the potential for serious functional impact. Significant decrease in range of motion has been documented in up to 20-42% of patients at one year post fracture. This lack of motion has been seen in patients treated both operatively and nonoperatively. Standard of care includes physical therapy, home exercise program and watchful waiting. Decreased range of motion can be very debilitating and greatly impacts activities of daily living (ADLs) including personal hygiene and feeding.

Adhesive capsulitis is a distinct clinical disorder causing similar symptoms of pain and stiffness but is not associated with fractures. Physical therapy including a home exercise program is the mainstay of treatment however, intra-articular steroid injections have been shown to provide significant short-term benefits regarding pain, range of motion (ROM), and shoulder function compared with other nonoperative treatments. Currently it is not known whether this treatment is applicable to patients with proximal humerus fractures as the pathophysiology differs. Applying results from this patient population to patients with proximal humerus fractures could lead to increased outcomes. Early intervention may also decrease time off work and help patients obtain peak outcome at an earlier time.

Approach

The goal of this study is to determine the feasibility of a large scale multi-centered randomized trial to evaluate the usefulness of this technique. The pilot study will take place in a single center. We will recruit patients with both operative and non-operative proximal humerus fractures during routine follow-up. Patients will be screened at 6 weeks after fracture treatment for the presence of decreased range of motion (defined as a loss of passive motion $> 30^\circ$ in 2 or more planes of movement). Those patients would then be randomized to receive standard of care (including physical therapy) or an ultrasound guided intraarticular cortisone injection in addition to standard of care. All research

participants will follow the same rehabilitation protocol included referral to physical therapy and a home exercise program. The time of inclusion in the study will be considered time zero. Clinical evaluation and validated functional outcomes will be completed initially (which will be considered "baseline") and at follow-up after 6, 12 and 24 weeks. Physical examination will document both passive and active range of motion (ROM) in standardized fashion. The primary outcome measure will be American shoulder and elbow society(ASES) score. This validated functional score is used for a multitude of shoulder pathologies including fractures, arthroplasty and rotator cuff disease. Secondary outcomes will be the visual analog score(VAS), passive ROM, return to work/activity and the abbreviated Constant-Murley score. The VAS was chosen because pain is often a significant component of post-operative stiffness and outpatient narcotics is a notoriously unreliable metric. Return to work or activity was chosen because there is a potential for decreased study effect over time. However, even if range of motion is not significantly different at one year, and earlier return to work would be considered a positive outcome. Considering the scope and goal of this trial and using a known MCID for the ASES score (primary outcome), a sample size of 20 patients in each group will be sufficient for this pilot study.

The most significant portion of the study cost will be paying for the study intervention (cortisone injection). We believe that standard of care for these fractures includes physical therapy and home exercise program but does not include an intraarticular injection. Therefore, in order to limit any potential harm to patients enrolled in the study, we have opted to pay any out of pocket expenses for the intervention. We have negotiated a fee reduction (52.3%) with the radiology department which represents approximately 680\$ per patient. The other significant cost will be the hiring of a temporary research assistant who will help recruit patients and document functional outcome scores. This person will be present 3 days per week during orthopedic trauma clinics. Based on fracture incidence at our institution, we believe that recruitment should be reached in 6-8 months. We have therefore budgeted for 12 months to account for missed recruitment/seasonal variability. All budget requirements above the funds provided in this grant will be paid for by a matched departmental research fund. IRB approval will be obtained prior to the grant period start. If any significant changes are required by the IRB committee, these will be communicated to the CLEAR funding directors.

With expected results 18-24 months after the study start date, we hope to move to a multicentered study within 36 months. We have already identified 3 other potential sites and will be ready to start relatively quickly after. Once the pilot study has begun and we have preliminary data showing the efficacy of the protocol, we will begin applying for funding for the full trial.

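### The outcome list plans no recording of complications by arm for an added injection whose applicability to fracture patients the protocol calls unknown

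*Protocol*

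**What the plan says.** **Evidence base (Background and Significance).** The benefit of intra-articular steroid is taken from adhesive capsulitis, which the protocol describes as a separate disorder unrelated to fractures. For fracture patients it says: "Currently it is not known whether this treatment is applicable to patients with proximal humerus fractures as the pathophysiology differs".

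**Population and exposure (Approach).** "We will recruit patients with both operative and non-operative proximal humerus fractures during routine follow-up". Screening is 6 weeks after fracture treatment. The injection is added to standard of care in one arm. The paragraph on costs confirms that standard of care "does not include an intraarticular injection".

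**Outcomes (Approach).** "The primary outcome measure will be American shoulder and elbow society(ASES) score". "Secondary outcomes will be the visual analog score(VAS), passive ROM, return to work/activity and the abbreviated Constant-Murley score". Assessments are at baseline and at 6, 12 and 24 weeks. The physical examination is described as documenting range of motion, and the research assistant's data task is to record functional scores.

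**Harm (Approach, paragraph on costs).** The word appears once, about money: "in order to limit any potential harm to patients enrolled in the study, we have opted to pay any out of pocket expenses".

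**Next step (Approach, final paragraph).** Funding applications for the full trial are to start once the pilot is under way and there is preliminary evidence of efficacy. No other condition is named.

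**Size (Approach).** "a sample size of 20 patients in each group will be sufficient for this pilot study".

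**The concern.** The pilot exists to inform a larger multicentre trial. By the protocol's own account, the injection is an extra exposure for these patients and its applicability to them is an open question. An obvious thing to learn from the injected arm is whether complications turn up, and how their number compares with the control arm. The outcome list contains nothing that would record this.

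Which outcomes are collected is protocol content. A statistical analysis plan can decide how to tabulate complications, but it cannot recover events that nobody asked about. If events come to light only when a patient or clinician happens to mention them, they may be noted more readily in the injected arm, because that arm received the study procedure. A count pieced together afterwards would then not be comparable between arms.

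If the list is followed as written, the team would come to plan the full trial with functional scores by arm and no planned complication count by arm.

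**Working it through.** **Step 1. Check each listed outcome against the question of how many patients in each arm had a complication.**

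| Outcome | What it can show | Counts events by arm? |
|---|---|---|
| ASES (primary) | Better or worse function and symptoms | No |
| VAS | More or less pain | No |
| Passive range of motion | Gain or loss of motion | No |
| Return to work/activity | Earlier or later return | No |
| Abbreviated Constant-Murley | Better or worse function | No |

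All of these can move in the unfavourable direction, so they are not blind to harm. None of them says that an event took place, what it was, or how many patients had one.

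**Step 2. The plan's own figure.** The only figure used here is 20 per group. It cannot be reproduced, because the protocol refers to an ASES MCID without giving its value, an SD, an alpha level or a power. Worked backwards under an assumed two-sided 5% level and 80% power, it implies a standardised difference of (1.960 + 0.842) × √(2/20) = 0.89. This does not bear on the present point. The 20 is taken as given, as the denominator for complications in the injected arm.

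**Step 3. What a complication count in 20 injected patients could show.** Inputs: n = 20 (Approach), all injected and all followed (assumption); true complication rate p (assumption, since the protocol gives none).

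Chance of seeing at least one event = 1 − (1 − p)^20:

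| Assumed p | Calculation | Chance of at least one event |
|---|---|---|
| 1% | 1 − 0.99^20 | 18% |
| 2% | 1 − 0.98^20 | 33% |
| 5% | 1 − 0.95^20 | 64% |
| 10% | 1 − 0.90^20 | 88% |

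Exact upper limit when no events are seen:

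- two-sided 95%: 1 − 0.025^(1/20) = 16.8%
- one-sided 95%: 1 − 0.05^(1/20) = 13.9%

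With one event in 20, the exact two-sided 95% interval is 0.1% to 24.9%.

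**Step 4. What it could not show.** The number of event-free injected patients needed to exclude a rate p (one-sided 95%) is ln(0.05)/ln(1 − p), rounded up. For p = 5% this is 59, and for p = 2% it is 149. Both are well beyond 20.

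A planned count in this pilot would therefore be likely to reveal a common complication, but could not show that an uncommon one is rare.

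**The case against.** **The aim is feasibility, and 20 patients cannot establish safety.** This stands. A reader might infer that the omission is what stops the pilot from saying whether the injection is safe enough to take further. Step 4 does not support that: with the outcome added, the pilot still could not say so. The point is only that a useful descriptive record is not planned.

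**The Background sentence is about applicability.** This also stands. A reader might take it to mean that the injection is untested in fracture patients, or that the protocol itself identifies complications as the main unknown. It says neither, and the sentences around it concern benefit. Infection and re-operation are examples supplied in this review. The protocol names no complication.

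**The scores can show harm, and clinical evaluation is planned at every visit.** This stands in part. It would be wrong to say that the outcomes can register only benefit, because a common harm affecting pain or function would tend to show by arm. But the examination is specified as range of motion, and nothing requires the same questions about events in both arms.

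**Adverse events may be recorded under the IRB submission or another document.** This is possible. The protocol says IRB approval is still to be obtained and may bring changes, and consent pages are not available here. The text therefore does not show that safety oversight is absent, and this point does not claim it. Such a record would still not be a stated outcome of this protocol, nor part of the step to the full trial.

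**No progression criteria are given at all.** This is true, so the lack of a place for safety belongs to a wider gap. The protocol does name efficacy, however, and complications could be named beside it for the cost of one sentence.

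**Conclusion.** The point holds as a modest, inexpensive improvement. The protocol fixes an outcome list with no count of complications by arm, for an intervention it describes as additional to standard of care and of unknown applicability to these patients. It also ties the move towards the full trial to efficacy alone.

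The loss is limited to descriptive information. At assumed true rates of 5% or 10%, the pilot would have a 64% or 88% chance of seeing at least one event among 20 injected patients. No events would exclude only rates above 16.8% (two-sided 95%; 13.9% one-sided). These figures assume that all 20 are injected and followed to 24 weeks; with fewer, the limits are wider.

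A reader might also infer that the injection is unsafe, or that the full trial will go ahead without regard to safety. The protocol supports neither. It contains no evidence on complication rates, and its last paragraph speaks of applying for funding, not of a final decision to expand.

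**What to change.** Add one item to the secondary outcomes in Approach:

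*Complications and adverse events through 24 weeks, asked in the same way in both arms at 6, 12 and 24 weeks, reported as counts by arm with exact two-sided 95% intervals.*

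Add one sentence to the final paragraph of Approach, saying that these counts will be considered alongside the efficacy data before moving to the full trial, and that with 20 injected patients they are descriptive.

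The visits are already scheduled, so the cost is a short checklist and a few minutes of data entry per visit. Treatment, sample size and the primary outcome are unchanged.

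### Feasibility is the only stated objective, but none of the five named outcomes measures it

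*Protocol*

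**What the plan says.** The Aim(s) section of the protocol states: "The primary objective of this study is to determine the feasibility of performing a large scale trial". The Approach repeats the purpose and adds that the later trial would be multi-centre: "The goal of this study is to determine the feasibility of a large scale multi-centered randomized trial". No other objective is given.

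Further on, the Approach fixes the outcomes. The primary one is ASES: "The primary outcome measure will be American shoulder and elbow society(ASES) score". The others are listed as follows: "Secondary outcomes will be the visual analog score(VAS), passive ROM, return to work/activity and the abbreviated Constant-Murley score". Assessments are at baseline and at 6, 12 and 24 weeks. The sample size rests on the same score: "Considering the scope and goal of this trial and using a known MCID for the ASES score (primary outcome), a sample size of 20" per group. The MCID is not stated.

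The budget and timeline text at the end of the Approach holds the only statements close to a feasibility measure. One is a forecast: "we believe that recruitment should be reached in 6-8 months". The other is the allowance built on it: "We have therefore budgeted for 12 months to account for missed recruitment/seasonal variability". The same text plans a research assistant on three clinic days per week, who is to help recruit and record functional scores. It also says that full-trial funding will be sought once the pilot has started and early data show the protocol's efficacy.

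**The concern.** A primary outcome should answer the primary objective. Here the objective asks whether a large trial can be run, while the primary outcome measures how patients' shoulders function. The protocol itself fixes both, so this is not a matter left to an analysis plan.

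At stake is what the pilot can report. Recruitment speed and retention will be visible in any case. The eligible share and the consenting share will not be, unless someone counts the patients who were screened and not randomised. The protocol prescribes screening at 6 weeks but does not ask for those counts. An analysis plan written later cannot recover denominators that were never recorded, and the full trial needs them to plan its number of sites and its duration.

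**Working it through.** **1. Objective against outcomes.** The question for each named item is whether it measures feasibility.

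| Item in the protocol | Status given | Measures feasibility? |
|---|---|---|
| ASES | primary outcome | no, functional score |
| VAS | secondary | no, pain |
| Passive ROM | secondary | no, clinical |
| Return to work/activity | secondary | no, functional |
| Abbreviated Constant-Murley | secondary | no, functional |
| 6-8 months to recruit | planning belief | could, but not named as an outcome |
| 12 months | budget allowance | could, but not named as an outcome |

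None of the five named outcomes addresses the objective.

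**2. The sample size of 20 per group.** Reproducing it would need an MCID value, an SD, an alpha and a power. None is given, so the figure is neither confirmed nor refuted.

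**3. What the recruitment forecast implies.** Two groups of 20 make 40 patients.
- 40/6 = 6.7 per month and 40/8 = 5.0 per month
- 40/12 = 3.3 per month over the budgeted period

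Assume Poisson recruitment that stops at the 40th patient after T months. The 95% limits for the monthly rate are the 2.5% and 97.5% points of chi-square with 80 df, divided by 2T. Halved, those points are 28.58 and 53.31.
- T = 6: 4.8 to 8.9 per month
- T = 8: 3.6 to 6.7 per month
- T = 12: 2.4 to 4.4 per month

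**4. Whether the forecast could serve as a pass/fail cut.** Suppose the true rate is exactly 5.0 per month. The expected count in 8 months is 40, and P(Poisson(40) ≤ 39) = 0.48. A site performing exactly as forecast would miss an 8-month target about half the time. The same holds at 3.33 per month over 12 months, where the expected count is again 40.

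**5. Precision of proportions.** The Wilson 95% limits are [p + z²/2n ± z√(p(1−p)/n + z²/4n²)] / (1 + z²/n), with z = 1.96.
- For 26/40: p = 0.65; numerator 0.65 + 0.0480 ± 1.96 × √(0.005688 + 0.000600) = 0.6980 ± 0.1554; denominator 1.0960. Limits 49.5% to 77.9%, so the lower one is 15.5 points from the estimate. This is the widest case at n = 40.
- Exact (Clopper-Pearson) limits at n = 40 reach 16.7 points. The widest case is 25/40 = 62.5%, with limits 45.8% to 77.3%.
- In one arm of 20, Wilson limits reach 22 points. The widest case is 14/20 = 70%, with limits 48.1% to 85.5%.

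The eligible and consenting shares have denominators other than 40. The protocol does not give them, so their precision cannot be computed.

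**The case against.** The best defence is that this is a pilot, and rehearsing the main trial's primary outcome in a pilot is ordinary practice. The sample-size sentence appeals to the trial's scope and goal, and that goal is feasibility. The forecast can be checked against what happens, and a short protocol may leave progression thresholds to an analysis plan that is not shown.

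Much of this stands. The absence of thresholds is therefore not the point made here. But the text does not say that ASES is only being rehearsed, and if it did, the objective would still have no outcome. The forecast is worded as a belief and serves only to support a 12-month budget.

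Three stronger readings are tempting, and the protocol does not support them:
- **That 20 per group is too few.** Too little is stated to test this. Moreover, "Clinical evaluation and validated functional outcomes will be completed initially", so a baseline-adjusted analysis is possible and an unadjusted power figure could mislead.
- **That moving to the full trial depends on a treatment effect.** The sentence about the protocol's efficacy may refer to workable procedures. It is ambiguous and proves neither reading.
- **That the 6-8 and 12 months should become go/no-go limits.** The protocol does not set them as such, and step 4 of the working shows how poorly a hard cut would perform.

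It is also fair to say that screening counts might be kept anyway. The protocol simply does not ask for them.

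**Conclusion.** The concern holds as a mismatch between objective and outcomes, and it should be fixed. All five named outcomes are clinical or functional and the sole objective is feasibility, so the primary result as planned does not answer the primary question. This conclusion comes from the text alone and needs no numerical assumption.

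The figures in the working bear only on how a feasibility result should be reported. They rest on all 40 patients being enrolled and, for the rates, on Poisson recruitment. They show that 40 patients give a usable but imprecise answer, which argues against hard cuts. The trial can run as it stands; what is missing is a named answer to its own question.

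**What to change.** **Outcomes (Approach).** Name these as the primary outcomes:
1. Recruitment per month, reported with its 95% CI against the protocol's own forecast of 5.0-6.7, with no hard go/no-go cut at those figures.
2. The share of patients screened at 6 weeks who meet the ROM criterion.
3. The share of those who consent.
4. Receipt of the allocated treatment.
5. Completeness of ASES at 24 weeks.

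Keep ASES as the leading clinical outcome. Report it as an estimate with a 95% CI, and give its SD for planning the full trial.

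**Screening log.** The research assistant already planned keeps a log of patients screened, eligible, consenting and randomised. It covers the three clinic days per week that this person attends, and the report should say so.

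**Progression.** The sponsor sets any limits before enrolment, allowing for the imprecision of 40 patients. If precision is quoted, name the method and the denominator: up to about 15.5 points from the estimate (Wilson) or 17 (exact) among 40, and up to about 22 points (Wilson) in one arm of 20. Do not apply the figures for 40 to shares of screened or eligible patients.

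**Funding sentence (end of the Approach).** If the early data meant there are feasibility data, say so.

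**Cost.** No extra patients or visits. There is a small logging task. The primary outcome changes, so this is more than an edit of wording, and the pilot is no longer presented as an efficacy result.

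### Does leaving the primary ASES visit unnamed among 6, 12 and 24 weeks call for a change to this pilot protocol?

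*Protocol*

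**What the plan says.** The Aim(s) section sets the primary objective as to "determine the feasibility of performing a large scale trial". The Approach section then fixes the outcome measure: "The primary outcome measure will be American shoulder and elbow society(ASES) score". Assessments take place at baseline, which is the time of inclusion, "and at follow-up after 6, 12 and 24 weeks". Neither section says which of the three follow-up scores is primary, whether the score is taken as a value or as a change from baseline, or whether the visits are combined.

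The sample-size sentence in Approach begins "Considering the scope and goal of this trial and using a known MCID for the ASES score (primary outcome" and arrives at 20 patients per group. It ties the minimal clinically important difference (MCID) to no visit and gives no value for it.

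Two places bear on whether the visits are interchangeable. Background and Significance reports that in adhesive capsulitis steroid injection gives "significant short-term benefits regarding pain, range of motion (ROM), and shoulder function". Approach, speaking of this study, gives a possible fading of the effect as its reason for including return to work or activity as a secondary outcome.

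On timing, Approach says "we believe that recruitment should be reached in 6-8 months" and "We have therefore budgeted for 12 months". Results are expected 18 to 24 months after the start. The search for full-trial funding is to begin at this point: "Once the pilot study has begun and we have preliminary data showing the efficacy of the protocol".

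**The concern.** An outcome measured three times without a chosen visit is only partly defined. If the injection speeds recovery but the groups later converge, a 6-week difference and a 24-week difference answer different questions, and the authors themselves allow for that pattern. A reader could fear two consequences.

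The first is selection: whichever visit looks best could be presented as the primary result. The second is timing: if ASES data are shown to funders while the pilot is still running, the visit on show would be set by which data happen to exist, and early on these are week-6 scores. If a full trial were then sized on an early difference but judged at a later visit where the difference is smaller, it would be too small.

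**Working it through.** **The plan's own figure.** The 20 per group can be neither reproduced nor called wrong, because the protocol gives no MCID value, standard deviation, error rate or power. Under an assumed two-sided 5% level and 80% power, 20 per group detects a standardised difference of (1.960 + 0.842) × √(2/20) = 0.886. This figure does not depend on the visit; a visit would enter only through the standard deviation, which is not stated.

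**How much of an early look would be week-6 data.** Inputs from Approach: 40 patients; visits at w = 6, 12 and 24 weeks; recruitment over 6 to 8 months, with 12 months budgeted. Assumed: even recruitment, no losses, visits on schedule. The number of patients with the week-w score at calendar week t, when recruitment lasts T weeks, is 40 × (t − w)/T, not below 0 and not above 40.

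| Look | T (weeks) | 6-week | 12-week | 24-week | 6-week share of all scores |
|---|---|---|---|---|---|
| Halfway, 6 months | 26.1 | 10.8 | 1.6 | 0 | 10.8/12.4 = 87% |
| Halfway, 8 months | 34.8 | 13.1 | 6.2 | 0 | 13.1/19.3 = 68% |
| End, 6 months | 26.1 | 30.8 | 21.6 | 3.2 | 30.8/55.6 = 55% |
| End, 8 months | 34.8 | 33.1 | 26.2 | 12.4 | 33.1/71.7 = 46% |
| End, 12 months | 52.2 | 35.4 | 30.8 | 21.6 | 35.4/87.8 = 40% |
| Follow-up complete | any | 40 | 40 | 40 | 40/120 = 33% |

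From week 24, while 6-week scores are still accruing, the share is (t − 6)/[(t − 6) + (t − 12) + (t − 24)] = (t − 6)/(3t − 42). It equals one half at t = 30. Counting each patient's latest score instead, between weeks 12 and 30 and while 6-week scores are still accruing, the share whose latest score is the 6-week one is 6/(t − 6), which is one half at t = 18. So preliminary data are mainly week-6 data before about week 30 by the first count, or before about week 18 by the second, and not after.

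**When all 24-week scores exist.** Recruitment of 6, 8 or 12 months plus 24 weeks (5.5 months) gives 11.5, 13.5 or 17.5 months. All three fall before the 18 to 24 months at which results are expected.

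**Selection among visits.** If three tests at an assumed two-sided 5% level were run and any one could be claimed, the chance of at least one false positive is 1 − 0.95³ = 14.3% if they are independent. By simulation it is about 12.5%, 10.9% and 8.4% at assumed correlations of 0.5, 0.7 and 0.9. The protocol states no test and no error rate, so these figures describe a hypothetical confirmatory use.

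**Undersizing of the full trial.** Sample size varies with the inverse square of the difference. If the 24-week difference were 50% to 75% of the 6-week one (assumed), a trial sized on week 6 would have 0.50² = 25% to 0.75² = 56% of the patients needed at week 24. This only squares an assumed decline. It also needs a full trial sized on the pilot's observed early difference, which the protocol does not say. The only sizing basis it mentions, and that for the pilot, is a known MCID, which does not depend on any observed difference.

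**The case for a change.** The strongest case for a change is that the protocol, not a later document, declares the primary outcome and links the sample size to it, so the protocol should complete the definition. The authors foresee a fading effect and use that to justify a secondary outcome, yet leave open when the primary one is judged. Naming a visit would take one sentence and add no patient or assessment. Even a 24-week choice fits the stated timetable.

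Much of this stands as description. No visit is named, the visits are not interchangeable, and settling the matter before outcome data are seen is good practice.

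What does not stand is the consequence. The funding sentence speaks of the efficacy of the protocol, not of the injection. With a feasibility aim, workability is at least as natural a reading, and on that reading the point about early data falls away. Even on the other reading no date, patient count or visit is fixed, and a look near the end of recruitment would already hold 22 to 31 twelve-week scores. The adhesive capsulitis evidence is weak support for a time course here, since Background and Significance calls it a distinct disorder and says that transfer to fractures is unknown.

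The proposed sentence would not correct anything either. It would ask the sponsor to record a choice, without any ground in the protocol for preferring one visit, and only if the analysis plan has not already done so.

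**Conclusion.** No change is needed. The omission is genuine, but it is missing detail of a kind that an analysis plan commonly fills, for example by naming one visit or by a repeated-measures summary with the other visits as supportive. That plan may exist and is not shown. No stated number, test or rule in the protocol is wrong because of it, and the feasibility objective does not depend on it.

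The worry about preliminary data is limited to an early look: 6-week scores dominate only before about week 30, and their share falls to between 40% and 55% at the end of recruitment and to 33% at the end of follow-up. These figures rest on even recruitment of 40 patients without losses. No error rate and no loss of power can be attributed to this protocol, because it specifies neither a test nor the inputs to its sample size. The conclusion would differ for a confirmatory trial, where the primary visit has to be fixed before the data are seen.

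### Does the 12-month budget leave the 24-week visits of later recruits uncovered?

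*Protocol*

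**What the plan says.** All the relevant text is in the Approach section of the Protocol; the budget and timeline paragraphs at its end have no heading of their own.

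- **Size:** "a sample size of 20 patients in each group will be sufficient for this pilot study", so 40 patients in all.
- **Clock and visits:** "The time of inclusion in the study will be considered time zero", with assessments at baseline "and at follow-up after 6, 12 and 24 weeks".
- **Recruitment forecast:** "Based on fracture incidence at our institution, we believe that recruitment should be reached in 6-8 months".
- **Budget:** "We have therefore budgeted for 12 months to account for missed recruitment/seasonal variability".
- **Staffing:** one of the two main costs is a "temporary research assistant who will help recruit patients and document functional outcome scores", present in the trauma clinics 3 days a week.
- **Money beyond the grant:** a matched departmental research fund meets whatever the grant does not.
- **Results:** expected 18 to 24 months after the study starts.

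**The concern.** The only reason given for the 12 months is slow or seasonal recruitment. Follow-up takes 5.5 months after each enrolment, and nothing in that sentence allows for it. If the 12 months must hold both, then most or all of the apparent 4 to 6 months of slack (12 minus 8, and 12 minus 6) is already needed for follow-up.

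The 12 months also reads naturally as the assistant's period. Of the two main costs, the injection is priced per patient and only the assistant's cost depends on time. The assistant is also the person named to record the functional scores, which include the ASES score, the primary outcome. If the post stopped at month 12, the last ASES reading could be missing for later recruits, or be taken by someone else. In a pilot whose aim is feasibility, a gap caused by staffing could be mistaken for a finding about whether patients can be followed.

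**Working it through.** **Inputs from the Protocol, Approach:** 40 patients; recruitment in 6 to 8 months; budget of 12 months; follow-up of 24 weeks from inclusion; results at 18 to 24 months.

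**Assumptions, since no recruitment curve is given:** even recruitment from month 0, month 0 the same for the budget and the study, and no dropout.

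The 12 months is a rounded allowance without a formula, so there is no calculation of the plan's own to reproduce.

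**Step 1. Follow-up in months.** 24 × 7 = 168 days; 168 / (365.25 / 12) = 168 / 30.44 = 5.52 months.

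**Step 2. Latest enrolment with a 24-week visit inside 12 months.** 12 − 5.52 = month 6.48, which lies inside the 6 to 8 month forecast.

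**Step 3. 24-week visits after month 12.** If recruitment lasts R months, the last visit is at R + 5.52, and the late visits number 40 × max(0, R − 6.48) / R.

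| Recruitment R (months) | Last 24-week visit (month) | 24-week visits after month 12, of 40 |
|---|---|---|
| 6 | 11.5 | 0 |
| 7 | 12.5 | 40 × 0.52 / 7 = 3.0 |
| 8 | 13.5 | 40 × 1.52 / 8 = 7.6 |
| 10 | 15.5 | 40 × 3.52 / 10 = 14.1 |
| 12 | 17.5 | 40 × 5.52 / 12 = 18.4 |

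Over the protocol's own forecast the range is 0 to about 8. The figure of 18 arises only if recruitment uses the whole 12 months. In that case about 9 of the 12-week visits (40 × 2.76 / 12 = 9.2) and about 5 of the 6-week visits (40 × 1.38 / 12 = 4.6) also fall after month 12.

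**Step 4. Does the stated timeline hold these visits?** Take the 12 months as the allowance for recruitment, which is the reason given for it. Follow-up then ends at month 17.5. That is 18 − 17.5 = 0.5 months before the earliest results date and 24 − 17.5 = 6.5 months before the latest. With 8-month recruitment, follow-up ends at month 13.5, which is 4.5 months before the earliest date. Every case in the table fits.

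**Step 5. Is there a payer?** Yes: the departmental fund takes on requirements above the grant. No sentence ends the assistant's post at month 12.

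**Step 6. What would re-planning the assistant's time cost?** Suppose the post is 12 months at 3 days a week; the protocol does not state this contract. That is 12 × 4.348 × 3 = 156.5 days.

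- *Recruitment in 8 months:* it uses 8 × 4.348 × 3 = 104.4 days, leaving 52.1 days, or 52.1 / 24 = 2.2 days a week for the final 24 weeks.
- *Recruitment in 12 months:* the same days must cover 52.2 + 24 = 76.2 weeks, or 156.5 / 76.2 = 2.05 days a week throughout. That is about a third less clinic coverage (1 − 2.05 / 3 = 0.32), in exactly the case where recruitment is already slow.

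**The case for a change.** The best case for a change is that a payer and a distant results date do not make 12 months the right length for the job. The assistant is temporary and is the only person named to record the outcome scores. The cushion exists for slow recruitment, yet using all of it puts 18 of 40 final visits outside the budgeted period. The results date could even be read as showing the mismatch, since work is clearly expected beyond month 12 while the stated budget stops there. One sentence would settle it.

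Part of this stands. The reason given for the 12 months leaves out follow-up, and the text does not say who collects visits after month 12. It is also fair to read the 12 months as mainly the assistant's time.

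The rest is inference. That the post ends at month 12, and that nobody would collect later scores, is not written anywhere. Nor does the protocol say that the assistant is unaware of treatment allocation, so a change of collector cannot be said to lose blinding. It defines no retention target that late visits would spoil. The results date fits 12 months of recruitment followed by complete follow-up at least as well as it fits a mismatch.

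**Conclusion.** No change to the plan follows. The 12 months is justified by recruitment alone, and some 24-week visits fall after it unless recruitment ends by about month 6.5: none of 40 for 6-month recruitment, about 8 for 8 months and about 18 for 12 months. These counts assume even recruitment from month 0 and no dropout; a slow start or a seasonal pattern would shift them.

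A team that follows the protocol as written would still make these visits. The schedule requires them, a fund is named for costs above the grant, and the last visit comes by month 17.5 even with 12 months of recruitment. What is missing is a staffing detail: who records scores late in the study. It affects neither the design, the outcome definition nor the analysis, and the study team can settle it once the recruitment pace is known. Fixing the assistant's hours in advance would bring no clear gain, because it means either more paid time or fewer clinic days while patients are still being recruited.
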